To our knowledge, so far, no clinical trial has been performed prospectively to quantify the viral reservoir in order to identify patients in whom cART could safely be interrupted. We will therefore prospectively evaluate about 640 cART treated HIV-1 positive patients in order to select a subgroup of individuals with extremely low HIV reservoirs, defined as an undetectable total HIV DNA and cell-associated HIV RNA (see section 5.1.3 for details) (first strategic goal). In those patients harboring low HIV reservoir, an analytical treatment interruption will be proposed (second strategic goal). Clinical and laboratory parameters (including VOA at baseline) of ensuing controllers and non-controllers (PTC vs. non-PTC) should allow us to identify predictors of functional cure after ATI (third strategic goal).

The innovative approach taken in this trial should help to take decisions on interrupting cART in future HIV cure strategies and lead to the identification of clinical and laboratory parameters correlating with PTC.

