### Step 4: Proportion of participants that will qualify for a treatment interruption.

The proportion of screened patient who may qualify for treatment interruption is based on preliminary research data generated in UZ Gent. It is evaluated at 7% of the screened patients corresponding to 45 potential patients to be included in the trial.

**Step 5: Proportion of patients that will accept to undergo a treatment interruption.** Although many patients have manifested their interest in participating into HIV trials, a

conservative and rational drop-out rate of 30% has to be taken into account in this project. Not all participants will be eager to interrupt a longstanding and most probably well supported treatment. On the other hand, the participants at this stage will be very motivated persons as they already underwent a stringent selection procedure (among others interview with psychologist) and heavy procedure (leukapheresis). The estimated number of participants would therefore be reduced to 32.

The proportion of post-treatment controllers is conservatively estimated at 5 to 15%, i.e. 2 to 5 out of the 32 study participants. (Of note this estimate is derived from data of PTC that were not selected based on a low HIV reservoir in contrast to the present study).

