### 8.3.4 Secondary endpoints

Safety of interrupting ART will be evaluated based on AEs and SAEs percentages together with a 95% Wilson confidence interval.

Reservoir replenishment and HIV viral load kinetics following ART interruption will be summarized in terms of medians and interquartile ranges. If present, pVL rebound will be represented graphically with a spaghetti plot.

Potential predictors of post-treatment control will be assessed by Fisher's exact test at 5% significance level.

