### 8.3.6 Multiplicity and Missing Data

Complete-case analyses will be performed.

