### 8.4 Sample size and power

It is estimated (section 4.3) that from all patients screened, 32 patients will finally enter the study and stop ART. Assuming a proportion of post-treatment control ranging between 5% and 15%, the width of the 95% Wilson confidence interval will be between 18 and 25 percentage points.

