4.3. Exploratory Objective

Potential predictors of post-treatment control (end of second part of the study) will be assessed by Fisher's exact test at 5% significance level (Example Table 6). The time to viral rebound will be assessed by survival analysis methodology, e.g. Kaplan-Meier estimates and curves (Example table 7). Potential predictors of viral rebound will be examined by single Cox regression models (Example Table 8).

4.4. Subgroup Analysis

No subgroup analyses will be performed in this study due to the small sample size .

5. Example Tables and Figures

Example Table 1: Patient Accounting

	n (%)
Screened	ХХ
Excluded	xx (xx %)
[add reason for exclusion]	xx (xx %)
	xx (xx %)
Enrolled to the first stage	xx (xx %)
- Completed the study	xx (xx %)
- Early withdrawals	xx (xx %)
- Lost to follow-up	xx (xx %)
- Consent withdrawal	xx (xx %)
Excluded from second stage	
Enrolled to the second stage	xx (xx %)
- Completed the study	xx (xx %)
- Early withdrawals	xx (xx %)
- Lost to follow-up	xx (xx %)
- Consent withdrawal	xx (xx %)

Example Table 2: Baseline Characteristics at Recruitment

	n (%)
Ν	XX
Epidemiological findings	
Age (yr): median (IQR)	xx (xx - xx)
Gender: male (%)	xx (xx)
female (%)	xx (xx)
Ethnicity: [add ethnic categories]	
Transmission route: [add categories]	
Duration of HIV infection (months/years): median (IQR)	
Total duration of antiviral treatment (months): median (IQR)	
Clinical findings	
Last antiviral treatment: PI+ NRTI	xx (xx)
NNRTI+NRTI	xx (xx)
II+ NRTI	xx (xx)
other	xx (xx)

xx (xx - xx)
xx (xx - xx)

Example Table 3: Summary of Primary and Secondary Analysis Results

	n/N (%, 95% Cl)
Primary analysis	
Number of participants with undetectable viral load (<50 HIV	xx/xxx
RNA copies/ml plasma) 48 weeks after interruption of ART	(xx; xx - xx)
Number of participants with undetectable viral load (<50 HIV RNA copies/ml plasma) at week:	
- 2	xx/xxx
	(xx; xx - xx)
- 4	xx/xxx
	(xx; xx - xx)
- 6	xx/xxx
	(xx; xx - xx)
- 8	xx/xxx
	(xx; xx - xx)
Secondary analysis	
Viral Reservoir at baseline (/10*6 PBMC's): median (IQR)	xx (xx - xx)
Viral Reservoir after TI (/10*6 PBMC's): median (IQR)	xx (xx - xx)
Viral load rebound by week (in copies/ml plasma): median (IQR)	
- 0 (baseline)	xx (xx - xx)
- 2	xx (xx - xx)
- 4	xx (xx - xx)
- 8	xx (xx - xx)

Example Table 4: Counts of patients (%) with Adverse Events by Body System and Preferred Term (Meddra)

	(N=xx) n(%)
Blood and Lymphatic System	xx (xx)
Anaemia	xx (xx)

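### With 2 to 5 controllers expected among 32, the 5% Fisher rule for predictors of control has little or no ability to detect one when controllers are few, and the 12 Cox tests for rebound have no multiplicity provision

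*SAP*

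**What the plan says.** Protocol 8.3.4: "Potential predictors of post-treatment control will be assessed by Fisher's exact test at 5% significance level". SAP 4.3 repeats this and names the time point: "Potential predictors of post-treatment control (end of second part of the study) will be assessed by Fisher's exact test at 5% significance level". It adds, for time to rebound: "Potential predictors of viral rebound will be examined by single Cox regression models". Only the Fisher sentence carries a significance level. The Cox sentence has none.

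Example Tables 6 and 8 list the same 12 characteristics, with a p-value column in each. In Table 6 only age and gender have levels. The other ten rows have none, and their layout is that of a continuous summary.

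On numbers, Protocol 8.4 expects that "32 patients will finally enter the study and stop ART". Protocol 4.3 adds: "The proportion of post-treatment controllers is conservatively estimated at 5 to 15%, i.e. 2 to 5 out of the 32 study participants". The same section notes that this estimate comes from patients who were not selected for a low reservoir.

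The Rationale (Protocol 1.2) says that comparing controllers with non-controllers "should allow us to identify predictors of functional cure after ATI (third strategic goal"). Protocol 8.3.6 has multiplicity in its title, but its whole text is: "Complete-case analyses will be performed". The SAP has no text on multiplicity. Protocol 3 and 3.3, SAP 2.2 and 4.3, and the titles of Tables 6 and 8 all call the predictor work exploratory.

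**The concern.** Fisher's test is discrete. When one outcome group has only two or three members, even perfect separation may not give a p-value below 0.05. A rule at 5% then returns no predictor because of the counts, whatever the biology. A reader who takes that as evidence against a predictor would be misled.

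The rebound analysis has the opposite risk. It runs one test per characteristic on the same list, with no statement of how 12 unadjusted p-values are to be read. An isolated small value could be taken as a finding.

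At stake is the third strategic goal in the Rationale, which is the comparison of controllers with non-controllers. The Cox models serve a different exploratory objective (SAP 2.2, rebound over time), so their error rate bears on that objective and not directly on predictors of control.

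**Working it through.** **Inputs.** N = 32 (Protocol 8.4); k = 2 to 5 controllers (Protocol 4.3); Fisher level 5% (Protocol 8.3.4, SAP 4.3). Fisher's test is taken as two-sided, because the documents do not say. The count of 12 characteristics comes from Example Tables 6 and 8.

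**The plan's own figures.** 643 x 7% = 45; 45 x 70% = 31.5, about 32; 32 x 5% = 1.6 and 32 x 15% = 4.8, so about 2 to 5. Wilson widths at 2/32 and 5/32 are 18.4 and 24.9 points, which agrees with Protocol 8.4: "the width of the 95% Wilson confidence interval will be between 18 and 25 percentage points".

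**Smallest attainable Fisher p.** Let a binary predictor be present in m of 32. If all k controllers fall in the group of m, the table has probability C(m,k)/C(32,k). At m = 16 the mirror-image table is equally likely, so the two-sided p doubles:

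- k = 2: 2 x 120/496 = 0.484
- k = 3: 2 x 560/4960 = 0.226
- k = 4: 2 x 1820/35960 = 0.101
- k = 5: 2 x 4368/201376 = 0.043

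An exact median split therefore cannot reach 5% with 2, 3 or 4 controllers. With 5 it can only if all five fall on the same side.

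The symmetry matters. With k = 4, moving to 15/17 gives a minimum p of 1365/35960 = 0.038.

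Enumerating every split m = 1 to 31:

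| Controllers | Smaller group must number | Splits that can never reach p<=0.05 |
|---|---|---|
| 2 | 2 to 7 | 19 of 31 |
| 3 | 2 to 12 | 9 of 31 |
| 4 | 2 to 15 | 3 of 31 |
| 5 | 2 to 16 | 2 of 31 |

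At the boundary for k = 2, m = 7 gives 21/496 = 0.042 and m = 8 gives 28/496 = 0.056.

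**How few controllers are likely.** With Binomial(32, p) at p = 5%: P(0) = 0.95^32 = 0.194 and P(1) = 32 x 0.05 x 0.95^31 = 0.326, so P(0 or 1) = 52%. With one controller only a 1/31 split can reach 5%, and with none there is nothing to test. P(at least 5 controllers) is 2%, 21% and 54% at true rates of 5%, 10% and 15%.

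**Cox models.** Assume each is read at 5%, no characteristic has a true effect, and the tests are independent. Then 1 - 0.95^12 = 0.460. If the two non-reference age levels count as separate tests, 1 - 0.95^13 = 0.487. Simulated Wald Cox tests at N = 32 with independent null covariates gave 48-49%.

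The figure depends on the assumptions:

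- Two correlated pairs, from r = 0.5/0.3 up to 0.9/0.7: 45% down to 43%.
- Common correlation of 0.1, 0.3 or 0.5 among all 12: 45%, 40% or 32%. An extreme 0.7 gives 23%.
- A level of 1% or 10% per test, if independent: 11% or 72%.

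**The case against.** Four points can be made for the plan.

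1. The work is labelled exploratory throughout and speaks of potential predictors. The primary analysis is a proportion with an interval and no hypothesis test, so no confirmatory error rate needs protecting. This stands, and it makes the point one of interpretation and reporting. It does not explain why a 5% rule is attached to the analysis with the smallest group, when SAP 4.2 forgoes formal testing for reservoir and kinetics and SAP 4.4 forgoes subgroups because of the small sample.

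2. A reader might infer that 5% is out of reach across the whole range of 2 to 5 controllers. The documents do not support that. With 4 or 5 controllers nearly all splits can reach it, and neither document prescribes a median split. The 2 to 5 is also an expectation that the protocol calls conservative, so there may be more.

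3. A reader might carry the 46% over to the Fisher tests, or take it as the chance that any reported Cox predictor is false. Neither follows. Fisher's actual size at these counts is below 5%, and zero for many splits. The 46% is a family-wise rate under a global null, at a level that the SAP does not state for Cox. Protocol 1.1 itself cites low HIV DNA as predictive of control, so a global null is not obviously the right state of the world.

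4. The 12 comes from example tables, and SAP 2.3 introduces the candidate variables as illustrations. That is correct, and it means the final number of tests could be larger or smaller.

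**Conclusion.** The concern holds in limited form. When controllers are few, the 5% Fisher rule has little or no ability to detect a predictor: 19 of 31 binary splits are out of reach with 2 controllers, 9 of 31 with 3, and an exact 16/16 split with up to 4. At a true control rate of 5% there is a 52% chance of 0 or 1 controller, where almost nothing can be tested. These results assume a binary predictor, a two-sided test and all 32 participants analysed. They do not cover the three-level age row.

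The missing cut-points for ten of the 12 Table 6 rows are a gap in their own right. Fisher's test cannot be run on those rows as laid out, and cut-points chosen after seeing the data would add undeclared flexibility.

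The absence of a multiplicity statement for the Cox models is a lesser matter: 46% under an assumed 5% level, independence and a global null, and about 32-45% with correlated pairs or a common correlation up to 0.5.

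The primary estimate is not affected.

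**What to change.** - Delete the 5% significance level from Protocol 8.3.4 and SAP 4.3.
- State in SAP 4.3 that Tables 6 and 8 are descriptive and hypothesis-generating, and that no p-value, small or large, will be read as identifying or excluding a predictor.
- List the individual baseline values of every controller, and give exact 95% confidence intervals for the odds ratios in Table 6.
- Keep the ten characteristics without levels continuous instead of dichotomising them for Fisher's test. An exact rank-sum test is one option. With 2 versus 30 and no ties its smallest two-sided p is 2/C(32,2) = 2/496 = 0.004. With one controller it is 2/32 = 0.0625, so this does not rescue that case. Baseline reservoir values may be tied, because entry requires undetectable total HIV DNA.
- Note under Table 8 that p-values are unadjusted across 12 characteristics. A false-discovery-rate column is optional, as is softening the wording on predictors in Protocol 1.2.

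The cost is a weaker claim about predictors, a few lines in the SAP, and a protocol amendment for the 8.3.4 wording. No new data are needed.
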